6.2. Treatment

The treatment period begins on the day that the subject receives the first dose of study drug (Cycle 1 Day 1) through the point at which the investigator determines that the subject will be permanently discontinued from study drug. Cycle 1 Day 1 must be no more than 28 days after the subject has signed the ICF and no more than 3 days after the date of enrollment. Dates for subsequent study visits will be determined based on this day and should occur within 3 days (+/-) of the scheduled date unless delayed for safety reasons. At Cycle 1 Day 1, results from screening visit evaluations should be reviewed to determine whether the subject continues to meet the eligibility requirements, as specified in the Protocol.

6.3. End of Treatment

When the subject permanently discontinues study drug, the EOT visit should be conducted. If the EOT visit coincides with a regular study visit, then the EOT evaluations will supersede those of that scheduled visit, and the data should be entered in the EOT visit in the eCRF. The subject should be encouraged to return for the follow-up visit.

6.4. Follow-Up

6.4.1. Safety Follow-Up

The safety follow-up period is the interval between the EOT visit and the scheduled follow-up visit, which should occur 30 to 35 days after the EOT visit (or after the last dose of study drug if the EOT visit was not performed). Adverse events and SAEs must be reported up until at least 30 days after the last dose of study drug, the date of the follow-up visit, or until toxicities resolve, return to baseline, or are deemed irreversible, whichever is longer. Reasonable efforts should be made to have the subject return for the follow-up visit and report any AEs that may occur during this period.

If a subject is scheduled to begin a new anticancer therapy before the end of the 30-day safety follow-up period, then the safety follow-up visit should be performed before new anticancer therapy is started. Once new anticancer therapy has been initiated, the subject will move into the survival follow-up period.

6.4.2. Disease Status Follow-Up

Subjects who discontinue study treatment for a reason other than disease progression will move into the disease status follow-up period and should be assessed every 9 weeks by radiologic imaging to monitor disease status. Every effort should be made to collect information regarding disease status until:

- The start of new antineoplastic therapy.
- Disease progression.
- Death.
- The end of the study.

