Tumor tissue will be evaluated through the central laboratory for confirmation of FGF/FGFR alteration status.

Blood samples for population pharmacokinetic analysis [REDACTED] will be collected at various timepoints throughout the study and analyzed at the central laboratory or designee.

Clinical Assessments:

Adverse event assessments, vital signs, electrocardiograms, physical examinations, ECOG performance status, comprehensive eye examinations, and tumor and disease response assessments will be performed by the investigative site.

An objective assessment of disease status will be performed at screening. Subsequently, disease status including RECIST radiological response assessment will be assessed every 2 cycles for the first 4 cycles and every 3 cycles thereafter. A central radiology group will be contracted to provide centralized reading on all assessments.

Estimated Duration of Participation:

Up to 28 days are allowed for screening, followed by continuous treatment in consecutive 21-day cycles as long as subject is receiving benefit and has not met any criteria for study withdrawal, and 30 days (+5 days) for safety follow-up following the last dose of the study drug. Subjects will be followed-up for overall survival following documented disease progression.

Estimated Number of Subjects:

Approximately 140 subjects will be enrolled (approximately 100 subjects in Cohort A, and approximately 20 subjects into Cohort B and Cohort C [US only] each).

Principal Coordinating Investigator: [REDACTED], MD

Statistical Methods:

Primary analysis will be performed on FGFR2 translocated subjects. Approximately 100 subjects with documentation of FGFR2 translocation from the central genomics laboratory are planned for the final analysis of the primary endpoint of ORR. With the assumed rates of 33% for the intervention, a sample size of approximately 100 subjects would provide > 95% probability to have a 95% confidence interval with lower limit of > 15% assuming 10% lost to follow-up. Up to 20 subjects will be enrolled in Cohorts B and C (US only), respectively, which will provide > 80% chance of observing at least 4 responders in each cohort if the underlying ORR is 30%.

The proportion of subjects with ORR and DCR will be estimated with 95% CI. The PFS, DOR, and OS will be analyzed by the Kaplan-Meier method. Descriptive statistics will be summarized for safety data.

Futility Analysis

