5.5. Withdrawal of Subjects From Study Treatment

5.5.1. Withdrawal Criteria

Subjects **must** be withdrawn from study treatment for the following reasons:

- The subject becomes pregnant.
- Consent is withdrawn. Note Subjects may choose to discontinue study treatment and remain in the study to be followed for progression and survival.
- Further treatment would be injurious to the subject's health or well-being, in the investigator's medical judgment. Subject would still be followed for progression and survival.
- The study is terminated by the sponsor.
- The study is terminated by the local health authority, IRB, or IEC.
- Unacceptable toxicity has occurred.
- Disease progression has been reported.
- Other antineoplastic treatment is initiated.

A subject **may** be discontinued from study treatment as follows:

- If, during the course of the study, a subject is found not to have met eligibility criteria but is receiving clinical benefit as per the investigator, the medical monitor, in collaboration with the investigator, will determine whether the subject should be withdrawn from the study. This includes cases where the local genomic testing result is positive for an FGF/FGFR alteration but the central genomic testing is not.
- If a subject is noncompliant with study procedures or study drug administration in the investigator's opinion, the sponsor should be consulted for instruction on handling the subject.

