6. STUDY ASSESSMENTS

All study assessments will be performed as indicated in the schedule of assessments ([Table 5](#)), and all laboratory assessments will be performed as indicated in [Table 6](#).

[Table 7](#) presents a summary of clinical laboratory analytes to be assessed. The order of assessments is suggested by the order of mention within the schedule. See Section 7 for instructions on each assessment. Further details of study procedures and assessments can be found in the study reference manual.

Table 5: Study Assessments

Procedure	Protocol Section	Pre-screening	Screening	Treatment				EOT	Follow-Up			Notes
				Days -28 to -1	Cycle 1		Cycle 2+		Safety	Disease Status	Survival	
			Day 1		Day 8 (± 3 days)	Day 15 (± 3 days)	Day 1 (± 3 days)					
			EOT + 30 (+5) days		Every 9 weeks	Every 12 weeks						
Genomic testing	7.1	X	X*								* May be done during prescreening or during screening.	
Informed consent	7.1	X	X									
Eye examination (includes slit lamp, visual acuity, funduscopy with digital imaging, and OCT)	7.5.5		X				X*	X				* Eye examination to be performed every 3 cycles (± 14 days) starting with Cycle 3 and/or as clinically indicated.
Review inclusion and exclusion criteria	3		X	X								
Demography and medical history	7.3		X									
Prior/concomitant medications	7.4		X	X	X	X	X	X	X			
Physical examination/ body weight, height	7.5.2		X*	X	X	X	X	X	X			* Comprehensive examination at screening, targeted physical examination thereafter.
Vital signs	7.5.3		X	X	X	X	X	X	X			
12-lead ECG	7.5.4		X	X		X	X	X	X			
ECOG status	7.6.2		X	X	X	X	X	X	X			

Table 5: Study Assessments (Continued)

Procedure	Protocol Section	Pre-Screening	Screening	Treatment				EOT	Follow-Up			Notes
				Days -28 to -1	Cycle 1		Cycle 2+		Safety	Disease Status	Survival	
			Day 1		Day 8 (± 3 days)	Day 15 (± 3 days)	Day 1 (± 3 days)					
			EOT + 30 (+5) days		Every 9 weeks	Every 12 weeks						
CT or MRI	7.6.1		X				X*	X		X**		* Every 2 cycles through Cycle 4; every 3 cycles thereafter starting with Cycle 7. ** Subjects who discontinue study treatment for a reason other than disease progression.
Review AEs	7.5.1		X	X	X	X	X	X	X			
Survival status	7.8.2										X*	* Once a subject has received the last dose of study drug, confirmed disease progression, or starts a new anticancer therapy.

CT = computed tomography; MRI = magnetic resonance imaging.

Table 6: Laboratory Assessments

	Protocol Section	Prescreening	Screening	Treatment				EOT	Follow-Up	Notes

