7.6. Efficacy Assessments

7.6.1. Tumor Imaging

Objective assessment of tumor status is required using appropriate disease-specific techniques, and a central radiologic facility will be used to determine responses and will be logged in to the eCRF. RECIST v1.1 ([Eisenhauer et al 2009](#)) will be used, and the recommended method for measuring and following tumor burden will be CT scan, to include the thorax, abdomen, and pelvis; the neck can be included if needed. Alternative modalities (eg, MRI) may be substituted for a CT scan at the discretion of the investigator, provided that the same modality is used throughout the study and that the methodology is consistent with RECIST v1.1.

The schedule for efficacy assessments will be at screening (this will be considered the baseline scan), every 2 cycles (every 6 weeks) for the first 4 cycles, every 3 cycles (every 9 weeks) thereafter, and then at EOT (if applicable). For subjects who discontinue treatment for reasons other than disease progression, every effort should be made to continue monitoring their disease status by radiographic imaging until 1) start of new anticancer therapy, 2) documented disease progression, 3) death, or 4) end of study, whichever occurs first.

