7.3.2. Progression-Free Survival

Progression-free survival is defined as the length of time from the start of the study drug (Day 1) until the earlier of death or PD by RECIST v1.1 as assessed by the independent centralized

radiological review committee. The date of PD will be the timepoint at which progression is first recorded. Censoring for PFS will follow the algorithm outlined in [Table 1](#), which is based on the FDA Guidance for Industry: Clinical Trial Endpoints for the Approval of Cancer Drugs and Biologics ([FDA 2015](#), [FDA 2018](#))

The number of subjects who progressed or died and the number of subjects censored will be summarized. The Kaplan-Meier estimate of median PFS will be presented with its 95% CI. The 95% CI will be calculated using the Brookmeyer and Crowley's method ([Brookmeyer and Crowley 1982](#)). The PFS analysis will be conducted for Cohorts A, B, and C, respectively.

Progression-free survival for Cohort A will be analyzed for each subgroup as described in Section [7.2.2](#), with the exception of renal/hepatic impairment. If there are sufficient subjects in each subgroup, forest plots of median PFS and its 95% CI for each subgroup will be provided.

Table 1: Evaluation and Censoring of Progression-Free Survival

Situation	Outcome	Date of Progression or Censoring
No baseline tumor assessment	Censored	Day 1
No adequate postbaseline response assessment	Censored	Day 1
Progression documented between scheduled response assessments	Progressed	Date of first overall response of progressive disease
No progression	Censored	Date of last adequate response assessment (not NE and not missing)
Study discontinuation for undocumented progression	Censored	Date of last adequate response assessment (not NE and not missing)
Study discontinuation for toxicity or other reason	Censored	Date of last adequate response assessment (not NE and not missing)
New anticancer treatment started	Censored	Date of last adequate response assessment (not NE and not missing) prior to starting of the new anticancer treatment
Death before first progressive disease assessment	Progressed	Date of death
Death between adequate assessment visits	Progressed	Date of death
Death or progression after more than 1 missed assessment	Censored	Date of last adequate response assessment (not NE and not missing)

NE = not evaluable.

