7.3.3. Duration of Response

For objective responders, DOR is the time from the first overall response contributing to an objective response as assessed by an independent centralized radiological review committee per RECIST v1.1, to the earlier of death or first overall response of PD occurring after the first overall response contributing to the objective response. Censoring of DOR will follow the same algorithm as the censoring of PFS (see Section [7.3.2](#)).

The total number of responders, the number of subjects who progressed or died, and the number of subjects censored will be summarized. The Kaplan-Meier estimate of median DOR will be presented with its 95% CI. The 95% CI for DOR will be calculated using the Brookmeyer and Crowley's method ([Brookmeyer and Crowley 1982](#)). The DOR analysis will be conducted for Cohorts A, B, and C, respectively.

Subgroup analysis of DOR for Cohort A will be conducted for renal impairment grade and for hepatic impairment grade if there are sufficient responders in each subgroup.

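### Central PFS and DOR have no scheduled imaging after a site-called progression that central review does not call (beyond any end-of-treatment scan), and no planned analysis tests the resulting upward bias in central DOR

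*Protocol*

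**What the plan says.** **Who reads the scans.** The Protocol synopsis (Clinical Assessments) says "tumor and disease response assessments will be performed by the investigative site", and also "A central radiology group will be contracted to provide centralized reading on all assessments". It gives no timing for the central read.

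**What ends treatment.** Protocol 5.5.1 lists among the reasons for mandatory withdrawal from treatment: "Disease progression has been reported". The reader is not named.

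**Who is still imaged.** Section 6.4.2 states: "Subjects who discontinue study treatment for a reason other than disease progression will move into the disease status follow-up period". Section 7.6.1 repeats the limit: "For subjects who discontinue treatment for reasons other than disease progression, every effort should be made to continue monitoring their disease status by radiographic imaging". The CT/MRI footnote for the disease-status column of Table 5 reads: "Subjects who discontinue study treatment for a reason other than disease progression". The synopsis (Study Schedule) and 7.6.4 carry the same restriction. Other subjects go to survival contact under 6.4.3. An end-of-treatment scan appears in Table 5, and 7.6.1 plans it where applicable.

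**How the endpoints are scored.** SAP 7.3.2: "Progression-free survival is defined as the length of time from the start of the study drug (Day 1) until the earlier of death or PD", with progression assessed by the independent central committee. SAP 7.3.3 uses the same committee for DOR and adds: "Censoring of DOR will follow the same algorithm as the censoring of PFS". SAP Table 1 censors at the last adequate assessment when there is no progression, and likewise when a subject leaves the study for undocumented progression. Deaths count as events, except after more than one missed assessment.

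**What else is planned.** SAP 7.4.2 adds investigator-assessed ORR, PFS, DOR and DCR, without confirmation of response. SAP 7.2.3 gives one sensitivity analysis, on the per-protocol population, for ORR.

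**The concern.** The event that stops imaging and the event that the endpoint counts may come from different readers. If the site calls progression and central review does not, the central endpoint is still open but scheduled imaging has ended. The subject is then normally censored at the scan that the site read as progression.

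Kaplan-Meier estimates assume that censored subjects have the same outlook as those still under observation. Subjects just judged by their physician to be worsening probably do not. Removing them without an event makes central PFS and DOR look longer. In a single-arm study these durability results are read beside the response rate, with no control arm carrying the same bias.

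**Working it through.** **The plan's own figure.** The plan states no design figure for PFS or DOR. Its one design figure for Cohort A concerns ORR: more than 95% probability that the lower 95% limit exceeds 15%, with a true rate of 33%, about 100 subjects and 10% lost.
- With n = 100 × 0.90 = 90, the smallest count whose Clopper-Pearson lower limit exceeds 15% is 21 (limit 15.1%; 20 responders give 14.1%).
- P(X ≥ 21 | 90, 0.33) = 98.3%. The figure reproduces and does not depend on this point.

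**Path of a discordant subject.**
1. The site reads a scan as progression. Treatment stops (5.5.1), and no central read is required first.
2. The reason for stopping is progression, so the 9-weekly disease-status imaging does not apply (6.4.2, 7.6.1, Table 5).
3. Central review reads the same scan as not progression. Apart from any end-of-treatment scan, nothing further is scheduled for it to read.
4. SAP Table 1 censors at the last adequate assessment, unless a death counts. Table 1 sets no order between its censoring rows and its death rows. It also does not say whether a scan that was no longer scheduled counts as missed.
5. DOR inherits the same rules.

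**Illustration of size.** Assumptions, none of them from the documents:
- Time to site-visible progression is exponential with median 26 weeks.
- A share q of site progressions is not called centrally.
- Central review would have called progression one scan later.
- No deaths occur in between.

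The scan grid is the protocol's: weeks 6, 12, 21, 30, 39 and so on.

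Weekly hazard λ = ln 2 / 26 = 0.02666. Probability of site progression in a 6-week interval: h₆ = 1 − exp(−6λ) = 0.1478. In a 9-week interval: h₉ = 1 − exp(−9λ) = 0.2133. Up to week 39 there are two 6-week and three 9-week intervals.

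Under the plan only the share (1 − q) counts as events, so in a large sample:

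S_plan(39) = [1 − (1 − q)h₆]² × [1 − (1 − q)h₉]³

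With imaging continued to central progression, discordant subjects fail one scan later:

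S_cont(39) = exp(−39λ) + q[exp(−30λ) − exp(−39λ)] = 0.3536 + 0.0959q

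| q | Plan | Continued imaging | Difference (points) | KM median, plan vs continued (weeks) |
|---|---|---|---|---|
| 10% | 39.7% | 36.3% | 3.3 | 30 vs 30 |
| 20% | 44.3% | 37.3% | 7.1 | 39 vs 30 |
| 30% | 49.5% | 38.2% | 11.2 | 39 vs 30 |
| 40% | 55.1% | 39.2% | 15.9 | 48 vs 30 |

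Differences are taken before rounding. A simulation of 20,000 subjects per scenario on the same grid agrees (40.0% vs 36.7% at 10%; 49.9% vs 38.4% at 30%).

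**Sensitivity of the illustration.**
- Median of 17 weeks: the formula gives differences of 3.2 points at 10% and 11.7 at 30%.
- Median of 35 weeks: 3.1 and 10.1 points.
- If 20% of discordant subjects count as events through early death, the simulated 26-week case gives 39.3 − 36.7 = 2.6 points at 10% and 47.3 − 38.4 = 8.9 points at 30%.

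The shift is upward in every case.

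**The case against.** **The reader is inferred.** Section 5.5.1 names no reader, and 7.6.1 has a central facility determining responses that are logged in the eCRF. Section 6.4.3 speaks of confirmed progression as one trigger for survival follow-up. The Independent Central Review Charter, which might provide for a central check before withdrawal, is not among the documents. This stands as a limit. Against it, the synopsis assigns response assessment to the site, no section requires a central read before withdrawal, and SAP 7.4.2 treats investigator and central readings as separate data.

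**SAP 7.4.2 already covers it.** Investigator PFS counts site progression as an event, so for PFS most of the effect can already be seen. For DOR it cannot: investigator DOR is computed in investigator responders without confirmation, a different set from the centrally confirmed responders.

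**Only descriptive secondary endpoints are touched.** True. SAP 7.1 has no efficacy hypothesis, and Protocol 4.2 disclaims historical comparisons.

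Four stronger readings are tempting, and the documents do not support them:
- *No later scan is possible and censoring is automatic.* An end-of-treatment scan is planned where applicable, survival contact continues, and some deaths count as events.
- *A centrally read first PR could never be confirmed.* If the PR was seen on an earlier scan, the scan that the site calls progression may itself confirm it centrally. Only a first PR on that same scan, with no usable end-of-treatment scan, is blocked. The confirmation rules are in the Charter.
- *The median is inflated by at most 1/(1 − q), that is 1.11 at 10% and 1.43 at 30%.* This rests on the same assumed rates and is not a bound on the scan grid. At 20% the formula gives 1.25, while the table gives 39/30 = 1.30. At 10% the median does not move.
- *The response-rate conclusion is weakened.* Nothing in the ORR design figure changes.

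**Conclusion.** The gap is real. A site-called progression that central review does not call ends scheduled imaging, apart from any end-of-treatment scan, while the central endpoint remains open. Unless a death counts, the subject is censored at the last adequate assessment. The censoring is informative, and central PFS and DOR are biased upward.

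The direction rests on two inferences: that reported progression can be a site reading, and that discordant subjects are closer to progression than those still followed. The size cannot be derived from the documents, which give neither a discordance rate nor an expected PFS. About 3 points on week-39 PFS at 10% discordance and about 11 at 30% are illustrations only. The clearest omission is for DOR, where no planned analysis tests the central estimate.

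**What to change.** **Main change (SAP).**
- In 7.3.3, add a sensitivity analysis of DOR in centrally confirmed responders. Site-reported progression that ended imaging counts as an event on its date.
- In 7.3.2, add the same analysis for central PFS.
- Report, by cohort, the number of subjects with site progression not called centrally.

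Cost: two or three extra outputs. The data are already collected, so this can be done even if enrollment is complete.

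**Optional change (Protocol).** For subjects not yet on new anticancer therapy, continue the existing 9-weekly imaging until centrally read progression. Both the entry wording and the stop wording need the qualifier, because 6.4.2 and 7.6.1 also end imaging at progression without saying whose. The edit must be consistent across the synopsis, Table 5, 6.4.2, 7.6.1 and 7.6.4. It adds some scans in discordant subjects and recovers only part of the information, since imaging still ends at new therapy. It concerns endpoint ascertainment only and leaves the treatment rules as they are.

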6.4.3. Survival Follow-Up

Once a subject has received the last dose of study drug, confirmed disease progression, or starts a new anticancer therapy, the subject moves into the survival follow-up period and should be contacted by telephone, email, or visit at least every 12 weeks to assess for survival status until death, withdrawal of consent, or the end of the study, whichever occurs first.

6.5. End of Study

The end of the study may be designated as the timepoint when all subjects have discontinued the study or the sponsor terminates the study.

6.6. Unscheduled Visits

Unscheduled visits may occur at any time as medically warranted. Any assessments performed during those visits should be recorded in the eCRF.

